### **Sample Size and Population**

The setting of this study is all four county hospitals that anchor care for patients in the Los Angeles County public healthcare system (LAC), which serves the largest, most ethnically diverse county in the United States. This system, often called the Safety Net, serves more than 10 million residents and provides healthcare to 700,000 people every year, and treats more than 300,000 emergency and trauma victims every year. Through an integrated network of hospitals, health centers and clinics, the LA County Health Services System makes medical and preventive care services accessible in communities across the county. According to LAC administrative databases, more than 50% of patients use a language other than English as their primary language and 63% of outpatients are uninsured.

A total of 500 subjects with the onset of ischemic stroke, hemorrhagic stroke, or transient ischemic attack (TIA) within the prior three months will be recruited from the following off-campus locations:

- (1) Los Angeles County Hospital + USC Medical Center (LAC+USC),
- (2) Rancho Los Amigos National Rehabilitation Center (Rancho Los Amigos),
- (3) Olive View-UCLA, and
- (4) Harbor-UCLA Medical Center.

No subjects will be recruited at UCLA.

Stratification variables are as follows, with 24 strata:

- Site (4 sites)
- Language (3: English, Spanish, other)
- Type of Stroke (2: ischemic/TIA, hemorrhagic)

## 1 STUDY OBJECTIVES

### 1.1. Primary Objectives

**Primary Objective #1:** To develop a *community-centered component* of a Chronic Care Model-based secondary stroke prevention intervention. This new component includes community health workers (CHWs) collaborating with healthcare system teams based at one of four Los Angeles County-Department of Health Services public “safety net” medical centers. CHWs - identified from the communities in which they serve - will receive specialized training and will conduct home visits to promote behavior change to address diet and physical activity risk factors, as well as assess for depression and social isolation. CHWs will use an existing, scalable mobile health platform specifically designed for care coordination and care teams to use by phone or iPad, to assist patients in tracking selected clinical measures (blood pressure, lipids, weight/BMI, physical activity), to promote behavior change. CHWs will communicate and liaison with the healthcare provider team. The community-based component will *also* include cultural- and stroke-specific adaptation of physical activity and self-management programs at local community venues including health education and senior centers.  
*Hypothesis: We will develop a culturally-tailored intervention to improve stroke risk factor reduction.*

**Primary Objective #2:** To test the impact of a sustainable Chronic Care Model-based intervention on control of systolic blood pressure (primary outcome), composite stroke risk, and each individual stroke risk factor (secondary outcomes), among 500 adults (over 90% minority) recruited “early” - during or shortly after hospitalization for an ischemic or hemorrhagic stroke or TIA - at one of the four Los Angeles County safety net medical centers. We will conduct a randomized trial of this intervention that includes the new, community-centered component developed in aim #1, and a “re-engineered” healthcare delivery system with nurse practitioners or physician assistants as care managers, distribution of home blood pressure monitors, group clinics, and a care management software system tailored to secondary stroke prevention and interfaced with the mobile health platform used by the CHWs, relative to usual care. We will include non-English speaking individuals from Hispanic, Chinese, and Korean racial and ethnic groups, and a broad range of stroke severity. We will analyze potential moderators (age, gender, stroke type and severity, education, country of birth/primary language, diabetes comorbidity, care team composition) to understand robustness of intervention impacts across levels of individual and health system characteristics. We will conduct a formative evaluation to continuously improve implementation, and will measure and analyze extent of intervention implementation, as it is delivered for up to 12 months after stroke or TIA through transition of patients into primary care. We will analyze potential mediators (life chaos, competing needs, medication adherence, knowledge of stroke risk factors, participation in self-management programs, social isolation, depression, health literacy, engagement with healthcare provider team, attitudes/health beliefs, self-efficacy, readiness to change, perceived risk, and perceptions of quality of interactions with provider) of the intervention’s impact, using both qualitative and quantitative methods.

*Hypothesis: Patients randomized to the SUCCEED intervention will achieve 8mm greater reduction in systolic blood pressure reduction and lower stroke risk scores at 1 year versus those randomized to usual care.*

### **Primary Objective #3:**

To conduct a cost analysis of SUCCEED from the perspective of the Los Angeles County Department of Health Services, using intervention costs, cost equivalents of associated utilization of county system resources, and cost equivalents of observed and projected vascular events. *We will also develop a financial plan and proposal for sustainability* of the intervention if it is effective, incorporating data on cost and utilization, to describe potential financial arrangements or approaches – including reimbursement strategies - to support the intervention model in the future and in other settings. We will also produce training materials and protocols for future dissemination.

*Hypothesis: If effective, the SUCCEED intervention will be sustainable because its community component was developed in partnership with the community and is culturally-appropriate, it will demonstrate a projected cost-offset from future vascular events averted, and intervention tools and training programs will be codified.*

### 1.2 Secondary Objectives

Not applicable

## 2 BACKGROUND

### 2.1 Rationale

Stroke is the fourth leading cause of death and the leading cause of adult disability in the United States, with well-documented and substantial disparities in the prevention and outcomes of stroke for blacks, Hispanics, and Asians relative to whites. The strongest predictor of a future stroke is a prior stroke or transient ischemic attack (TIA). Although the risk of stroke can be substantially reduced through control of modifiable risk factors including hypertension, diet, physical activity, and smoking, and through optimal management of diabetes and dyslipidemia there is abundant evidence that these risk factors are under optimal control in only a small proportion of stroke survivors, exposing hundreds of thousands of individuals each year to preventable death and disability from subsequent strokes. The situation is even more pressing among indigent, minority populations, in which knowledge about stroke is limited and barriers to accessing healthcare – transportation, healthcare-related costs, screening of phone communication due to concerns about immigration authorities, bill collectors, inability of healthcare providers to maintain current phone numbers due to patients use of prepaid phones that run out, beliefs about causes of stroke symptoms, unhealthy diets, lack of safe places to walk or local stores with fresh produce, homelessness, and many others - are formidable. Our group previously documented gaps in prevention care after stroke and analyzed barriers among the large, multi-ethnic indigent population in Los Angeles County, where out of the entire county's approximately 10 million residents spread over several thousand square miles, fewer than 30% are non-Hispanic whites.

Based on International Classification Codes (ICD) codes generated from the Los Angeles county Department of Health Services (LAC-DHC) database, there are over 1000 admissions of stroke per year at the four County anchor hospitals. This eligible population is more than 20% greater than in SUSTAIN due to the inclusion of hemorrhagic stroke. The eligibility is further increased by including more languages spoken by subjects.

**Table 2.** Stroke and TIA patients hospitalized in Los Angeles County, 2009-2011

Facility	Year	Stroke	TIA	Hemorrhagic Stroke	Total
		ICD: 433,434, 436	ICD:435	ICD: 430, 431	
Harbor-UCLA Medical Center	2009	250	65	72	387
	2010	218	58	72	348
	2011	250	57	59	366
Olive View Medical Center	2009	124	31	7	162
	2010	178	29	8	215
	2011	131	30	4	165
Rancho Los Amigos	2009	148	46	11	205
	2010	166	40	12	218
	2011	143	45	18	206
LAC+USC	2009	192	31	98	321
	2010	192	52	119	363
	2011	184	51	116	351
All Los Angeles County Safety Net Hospital	2009	714	173	188	1075
	2010	754	179	211	1144
	2011	708	183	197	1088

In addition to this eligible inpatient pool, outpatients who have had the onset of with a recent history of stroke or TIA are also eligible. Rancho Los Amigos is implementing a medical home model for uninsured patients with a recent stroke, so patients who were admitted elsewhere for their stroke can be fast-tracked to receive post-discharge follow-up care at Rancho Los Amigos.

Starting in 2010, Los Angeles County has implemented an Emergency Medical System (EMS) routing policy. Patients with acute onset of stroke symptoms within three hours are diverted to stroke certified centers. None of the four LAC hospitals have obtained this designation yet. However, we do not anticipate this to be a barrier to enrolling enough patients because the number of hospitalized stroke and TIA patients in 2011 remains above 1000.

[figure not shown]
## **2.2 Supporting Data ([name] will add SUSTAIN ABSTRACT you have until the end of this page)**

Our research team has designed and is implementing a chronic care model-based program called SUSTAIN (Systemic Use of STroke Averting INterventions) to improve the delivery of secondary stroke preventive services after hospital discharge. This care intervention includes group clinics, self-management support, report cards, decision support through care guides and protocols, and coordination of ongoing care. The first specific aim is to test via a randomized-controlled trial whether SUSTAIN improves blood pressure control among an analytic sample of 268 patients with a recent stroke or transient ischemic attack discharged from four Los Angeles County public hospitals. Secondary outcomes consist of control of other stroke risk factors, lifestyle habits, medication adherence, patient perceptions of care quality, functional status, and quality of life. A second specific aim is to conduct a cost analysis of SUSTAIN from the perspective of the Los Angeles County Department of Health Services, using direct costs of the intervention, cost equivalents of associated utilization of county system resources, and cost equivalents of the observed and predicted averted vascular events.

In this study, we build upon our experiences implementing SUSTAIN to enhance the access to community resources. These include the use of community health workers, mobile technology to synchronize information while in the field, and increasing access to self-management classes.

### 3 STUDY DESIGN

**Figure 1. SUCCEED Study Design**

The study design for SUCCEED trial is a multi-center, randomized controlled trial of a Care Management and Community Health Worker led intervention VS Usual Care to improve management of stroke risk factors. The outcomes of this study will be assessed by a blinded Research Assistant. Subjects will be enrolled in the RCT for a period of 1 Year. A diagram of the study is provided as shown in **Figure 1 to the left**.

We designate systolic blood pressure as the primary outcome for the purpose of sample size calculations. We will assess multiple relevant outcomes including all risk factors and a composite index, cost, quality of life, adverse consequences, moderators, mediators, and a range of metrics of intervention program implementation and participation.

## 4 SELECTION AND ENROLLMENT OF SUBJECTS

The inclusion and exclusion criteria for the SUCCEED RCT are shown below:

**Table 3.** Inclusion and Exclusion Criteria of RCT

Inclusion Criteria

 
Patients of LAC + USC, Rancho Los Amigos, Olive View-UCLA, or Harbor-UCLA with onset of ischemic stroke, hemorrhagic stroke, or TIA within the prior three months.
 

Exclusion Criteria

 
Age < 40 years
 
SBP < 120 mm Hg
 
Speaks language other than English, Spanish, Korean, Mandarin, and Cantonese
 
Cannot provide informed consent due to dementia or aphasia
 

### 4.1 Inclusion Criteria

4.1.1 *The disease or disorder under study, and how it is being documented (diagnostic methods, criteria for evaluation)*

Patients with onset of ischemic stroke, hemorrhagic stroke, TIA within the prior three months will be included in SUCCEED. Diagnosis is confirmed by referring clinician.

4.1.2 *Clinical indicators of current status, as measured with XX days of randomization.*

Not applicable

4.1.3 *Prior therapy, if any. Consider listing prior treatments. Consider listing the allowable duration for the specific population to be studied (treatment-naïve, treatment-experienced, or prior-treatment-failed “salvage subjects”)*

Not applicable

4.1.4 *Demographic characteristics*

Patients over 40 years of age will be included in SUCCEED. Patients will be included if they speak English, Spanish, Korean, Mandarin, or Cantonese.

### 4.2 Exclusion Criteria

4.2.1 *List any clinical contradictions. Specify grades of signs/symptoms*

Persons with language (aphasia) or cognitive difficulties are ineligible if they cannot communicate that they understand the study during the informed consent process.

4.2.2 *Clinical/laboratory indicators of current status, obtained within XX prior to randomization. List the specific tests to be performed and the narrowest acceptable range of laboratory values for exclusion, consistent for safety.*

Systolic Blood pressure > 120 mmHg

4.2.3 *Specify any exclusion related to pregnancy, lactation, or plans to become pregnant. Specify methods for assessing current status and willingness to use contraception, if applicable.*

Not applicable

4.2.4 *Use of excluded drugs, devices, etc. within XX days prior to entry*

Not applicable

4.2.5 *For drug studies: Allergy/sensitivity to study drugs or their formulations*  
Not applicable

4.2.6 *Specify any clinical (life expectancy, co-existing disease), demographic (age) or other characteristics that precludes appropriate diagnosis, treatment, or follow-up in the trial*

Young patients are excluded because the mechanism for their strokes is frequently not due to atherosclerosis (e.g. arterial dissections, congenital coagulation defects, etc), so the interventions in this proposal may not be as applicable to them. We will also exclude persons who already meet the primary outcome of SBP <120 mm Hg. We will not be able to translate written materials in languages other than English, Spanish, Korean, and Chinese. Patients who do not speak any of those languages will be excluded.

4.2.7 *Active drug or alcohol use or dependence that, in the opinion of the site investigator, would interfere with adherence to the study requirements.*

If the participant exhibited active drug or alcohol use or dependence that, in the opinion of the site investigator would interfere with adherence to study requirements, that participant would be excluded from the study.

4.2.8 *Serious illness (requiring systemic treatment and/or hospitalization) until subject either completes therapy or is clinically stable on therapy, in the opinion of the site investigator, for at least XX prior to the study. (List specific illnesses and acceptable time)*

Not applicable, hospitalized patients are being enrolled in the study.

4.2.9 *Inability or unwillingness of subject to give written consent.*

If a subject is unwilling to give written consent, they will be excluded from the trial. Persons with language (aphasia) or cognitive difficulties are ineligible if they cannot communicate that they understand the study during the informed consent process.

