### 9.3 Sample Size and Accrual

#### **Power Analysis**

Power Analyses was conducted with comparison of main outcomes (systolic blood pressure (SBP)) between the control and intervention arms. Based on availability of patients and our capacity, we plan to enroll 500 subjects from four senior centers. Using Intra-class correlation (ICC) of the four centers at 0.0085 level, attrition after the baseline between 20% to 30% level, mean SBP 141 mm Hg and standard deviation (SD) 20, three repeated measurements: baseline, 3 months, and 12 months (Brown and Prescott 2006), the underlying

statistical power of the study comes from two dimensions of observations: the number of unique subjects and the number of repeated measurements within a subject. Based on sample size and power analyses method proposed by Diggle et al. (1994) and Liu et al. (2005) for repeated measures analysis with a type I error of 0.05, type II error of 0.2 (or equivalent to power of 80%), 2.6 and 2.4 average data points for each subject (corresponding to 20% and 30% attrition respectively), and an auto-correlation at 0.2 level, the effective sample size will be 147 and 147 out of the planned 250 and 250 participants in each of the 2 arms (after adjusting for clustering effect), which will enable us to detect an effect size for SBP as small as 0.215 in standard deviation units or 4.29 mm Hg (for 20% attrition), and 0.253 in standard deviation units or 5.06 mm Hg (for 30% attrition).

The seminal work for moderator and mediator effect was from Baron and Kenny (1986). For potential moderators (e.g., age, gender, stroke type and severity, education, country of birth/primary language), we will test power of moderation using the most common measure of effect size  $f^2$  (Aiken & West, 2001), which equals the unique variance explained by the interaction term divided by sum of the error and interaction variances. Cohen (1988) has suggested that  $f^2$  effect sizes of 0.02, 0.15, and 0.35 are termed small, medium, and large, respectively. A more realistic standard for effect sizes with moderators might be 0.005, 0.01, and 0.025 for small, medium, and large, respectively.

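### Section 4.2.2 excludes SBP above 120 mm Hg, the reverse of Table 3 and Section 4.2.6; as written it would turn away about 85% of patients under the plan's own SBP assumptions

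*Combined protocol and SAP*

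**What the plan says.** The SBP entry rule appears in three places in the combined protocol and SAP:

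- **Table 3 (Section 4)** lists SBP below 120 mm Hg as an exclusion.
- **Section 4.2.2**, also under Exclusion Criteria, reads in full "Systolic Blood pressure > 120 mmHg".
- **Section 4.2.6** reads "We will also exclude persons who already meet the primary outcome of SBP <120 mm Hg".

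Two other sections depend on who enters. Section 9.3 bases the power analysis on "mean SBP 141 mm Hg and standard deviation (SD) 20". Table 1 in Section 9.2 includes the proportion of patients with BP under 120/80 in the primary outcome. Section 1.1 hypothesises an 8 mm greater SBP reduction with the intervention.

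**The concern.** The lines cannot all be followed. Section 4.2.2 turns away the patients whom Table 3 and Section 4.2.6 let in, and lets in those whom they turn away.

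This criterion decides who is randomized. Under Section 4.3.3 the research assistant measures BP to confirm eligibility. Section 6.2.1 places screening, baseline and randomization in one face-to-face meeting, and no separate eligibility review before allocation is described. Under Section 4.3.1 the eligibility requirements are also put on cards for house staff, so an error can reach referring clinicians at all four sites.

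A site working from Section 4.2.2 would recruit patients already at or below the systolic target. They have little SBP to lower, and nearly all would start at or under the systolic part of the 120/80 outcome. The contrast between arms would be diluted there. Section 9.5 also builds enrolment weights from eligible patients who decline. The direction of the rule defines that group, so mixed use across sites would carry into the weighted analysis.

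**Working it through.** **1. The rules side by side**

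| Source | Excluded | Left eligible |
|---|---|---|
| Table 3, Section 4.2.6 | SBP < 120 | SBP ≥ 120 |
| Section 4.2.2 | SBP > 120 | SBP ≤ 120 |
| All applied together | all except 120 | SBP = 120 only |

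**2. The plan's own figures, and whether the SBP rule enters them**

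Section 9.3 states no share of patients excluded. Its figures are detectable differences: 0.215 SD or 4.29 mm Hg at 20% attrition, and 0.253 SD or 5.06 mm Hg at 30%, with 147 effective subjects per arm, type I error 0.05 and 80% power. I took the test as two-sided. With first-order autoregressive correlation 0.2 (the plan gives "an auto-correlation at 0.2 level"), the variance of the mean of m measurements, in SD² units, is:

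- m = 3: V = (3 + 4 × 0.2 + 2 × 0.04)/9 = 0.4311
- m = 2: V = (2 + 2 × 0.2)/4 = 0.600

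Then d = (1.960 + 0.842) × √(2V/147):

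- m = 3: d = 0.2146 SD; × 20 = 4.29 mm Hg
- m = 2: d = 0.2531 SD; × 20 = 5.06 mm Hg

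Both stated figures reproduce. The mean of 141 appears nowhere in the formula, so correcting the SBP rule changes neither figure.

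(Outside this point: the match needs 3 and 2 whole measurements, whereas the plan gives "2.6 and 2.4 average data points for each subject". Also, 147 needs three clusters: 250/(1 + (250/3 − 1) × 0.0085) = 147.1. The four stated centres give 164.2.)

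**3. Share of patients each rule removes**

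Inputs are mean 141 and SD 20 from Section 9.3. Normality is my assumption, as is reading these values as describing patients before selection on SBP.

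- z = (120 − 141)/20 = −1.05
- Removed by Section 4.2.2: P(SBP > 120) = 1 − Φ(−1.05) = 85.3%
- Removed by Table 3: P(SBP < 120) = Φ(−1.05) = 14.7%
- Left if all are applied, with SBP rounded to whole mm Hg: P(119.5 to 120.5) = 1.1%

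Sensitivity of the 85.3%: a lognormal with the same mean and SD gives 85.8%, and a gamma gives 85.5%. Normal means of 138 to 144 with SDs of 18 to 22 give 79% to 91%.

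**4. Who would be enrolled**

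Truncating the same normal distribution at 120 gives:

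- Section 4.2.2 (at or below 120): mean 109.7, SD 8.8
- Table 3 (at or above 120): mean 146.4, SD 16.1

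Whatever the distribution, a sample with every value at or below 120 cannot have a mean of 141.

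**5. Scale against the patient pool**

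Table 2 counts 1,088 stroke and TIA patients hospitalised in 2011. Before age, language and consent, about 1,088 × 0.147 = 160 would pass Section 4.2.2, and about 1,088 × 0.853 = 928 would pass Table 3. Planned enrolment is 500.

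**The case against.** The best defence is that the intent can be recovered. Table 3 is itself introduced as the trial's criteria, and nothing ranks Section 4.2.2 above it. Section 4.2 consists of answers to template prompts, and the prompt for 4.2.2 speaks of a range of acceptable values. The line may therefore be an entry requirement under the wrong heading, or a one-character slip. Section 4.2.6 gives its direction with a reason, and the planning mean fits that direction. A site following 4.2.2 would be turning away nearly every hypertensive patient in a BP-lowering trial. Reasons for ineligibility are recorded and reported monthly by site (Section 4.3.3), and low enrolment is investigated, so a reversed rule would probably be noticed.

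The 85% can also be challenged. Section 9.3 gives no distribution shape and does not say whether 141 and 20 describe screened or enrolled patients. If they describe enrolled patients, the 14.7% for Table 3 has no meaning, because those patients have already been removed.

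Most of this stands, and it lowers the chance of harm. It does not remove the contradiction. The line is still listed as an exclusion, no other text overrides it, and monthly reports come after patients have been randomized. The uncertainty over 141 and 20 does not help Section 4.2.2 either: on the other reading it would exclude essentially everyone.

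**Conclusion.** The concern holds. Section 4.2.2 contradicts Table 3 and Section 4.2.6 on the direction of the SBP entry rule, and nothing elsewhere in the document resolves it. That conclusion needs no distributional assumption, nor does the finding that Section 4.2.2 is incompatible with a mean SBP of 141 among enrolled patients.

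The size, about 85% of candidates wrongly turned away, rests on rough normality and on mean 141 and SD 20 describing patients before selection on SBP. The range is 79% to 91% for nearby values, and essentially 100% if the figures describe enrolled patients. The harm depends on a site actually using Section 4.2.2, and I have not quantified the dilution of the treatment contrast. Because the line governs entry to a trial whose primary outcome is SBP, it must be corrected.

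**What to change.** Reconcile Section 4.2.2 with Table 3 and Section 4.2.6 so that the same threshold and direction appear in all three. The reason given in Section 4.2.6 and the planning mean in Section 9.3 are consistent only with the direction in Table 3. State explicitly whether a reading of exactly 120 mm Hg is eligible. Check that the house-staff cards and any screening form carry the same rule. It would also help to say in Section 9.3 whether the mean of 141 and SD of 20 describe screened or enrolled patients.

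The cost is a one-line protocol correction, plus a check of the recruitment materials. The sample size and the stated detectable differences are unaffected. If screening has already begun, compare the baseline SBP of randomized patients at each site with the reconciled rule and report any enrolled against it.
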